9.2 CBR as endpoints

Any treatment arm that was closed to accrual after the first stage analysis will be considered to be an inferior arm. The CBR rates of all arms with complete accrual of 28 evaluable patients will be estimated and used as additional reference for the determination of the winner arm to be considered for further study.

9.3 Other Endpoints:

Preclinical evidence show that mTOR inhibitor resistance may be due to increased survival pathway signaling activity with resultant addiction of the tumor cells to this pathway. The trial will explore the potential benefit of sequential versus concurrent initiation of mTOR inhibitor and Pasireotide. For this purpose, patients randomized to the single agent arms will be allowed to receive the 2-drug combination at the time of disease progression. Such patients may, however, remain on treatment only if they achieve disease stabilization or objective response at the end of

the first 2 cycles of 2-drug combination using the last imaging scan obtained while on the single agent therapy as the new baseline.

9.4 Correlative Study Analyses:

The expression of somatostatin receptor and mTOR pathway protein (S6, pS6, 4E-BP1, p-4E-BP1, eIF4e, Akt, pAkt, raptor, rictor, PRAS40, mSin1, FKBP38, IGF-R, IRS-1 and HIF1- α) in archival tissue and in fresh tumor biopsy obtained at the time of progression will be determined by immunohistochemistry and quantified by immunoscore as previously described.⁵² Differences in mean expression between the 3 treatment arms will be compared with ANOVA or Chi-Square test. Longitudinal analyses will also be conducted to investigate the association between the treatment arm and changes in circulating IGF-1 using ELISA assay and immunoscore of the listed proteins in progressing patients. The MIXED procedure of SAS will be used for the analyses.

10 Protocol amendments, or changes in study conduct

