3.3 Exploratory objectives

Correlate the level of expression of mTOR pathway signaling proteins in archival tumor tissue with the clinical activity of everolimus

Correlate the level of expression of somatostatin receptor expression and IGF1-R in archival tumor tissue with clinical efficacy of Pasireotide

Exploratory analysis of disease response based on histology and FDG PET uptake

4 Study design

This is an open-label, 3-arm, non comparative phase II clinical trial to study the single agent and combined efficacy of pasireotide and everolimus in patients with iodine refractory, differentiated (papillary, follicular and their variants) and medullary thyroid cancer. Patients will be randomly assigned to one of three arms to receive single agent pasireotide, everolimus or the combination of both drugs (Figure 4). Patient randomization will be stratified by histology, (medullary versus non medullary thyroid cancer). In order to explore the optimal schedule of administration,

patients who were initially randomized to the single agent arm will be allowed to receive the second agent at the time of disease progression. Such patients, however, may only proceed with the trial if they achieve disease stabilization or objective response at the end of the first 2 cycles of 2-drug combination and without experiencing any grade ≥ 4 hematologic or grade ≥ 3 non-hematologic toxicities. Everolimus will be administered once daily continuously on days 1 to 28; pasireotide will be administered as a long acting intramuscular depot injection given once every 4 weeks. One cycle will be defined as 4 weeks with response assessment with cross sectional imaging planned for the end of every even numbered cycle. Biochemical response will be assessed using serum-based tumor markers (Thyroglobulin, CEA, calcitonin) specific or informative for the histologic subtype of thyroid cancer. Patients will be evaluated at the end of cycle 1 and cycle 2, and subsequently after every 2 cycles along with restaging scans.

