The study design for this Phase II trial is a randomized screening design with multiple arms. A simple winner arm is selected only from the arms shown to be superior to the historical control. Between arms: Eligible patients will be randomly assigned to one of three arms to receive single agent pasireotide, everolimus or the combination of both drugs. Randomization is conducted with a block of 3 patients in order to balance the enrollment in each arm (The first of the 3 patients entered consecutively is randomly assigned to any of the 3 arms; the second patient is randomly assigned to one of the remaining 2 arms and the third patient to the last arm).

Within arms: Within each of the 3 arms, a Simon's 2-stage MinMax design is used. Eighteen evaluable patients will be enrolled into stage I. At least one objective response is required to proceed to stage II accrual of 10 additional patients for a total of 28 patients per arm. At least 3 patients must achieve objective response for the particular treatment arm to be considered worthy of further clinical evaluation in this disease.

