7.7 Exploratory biomarker assessments

7.7.1 Sample collection

Refer appendix B for details of sample collection, handling, preservation and shipping

Blood Sample Collection:

Blood samples will be collected at the indicated times into heparinized green top tubes (7 mls for PBMC collection - optional), red top tube (7 mls to obtain serum sample for ELISA assay). PBMC will be purified using standard Ficoll-Paque gradient centrifugation according to the instructions of the manufacturer (Amersham Pharmacia, Uppsala, Sweden). All samples must be stored away within 2 hours of collection by refrigeration at -70 to -80°C until ready for assay.

Paraffin-Embedded Tissue

Archival paraffin embedded tissue collected at the time of patient screening will be shipped to the lab of [name] at the Winship Cancer Institute. If the entire paraffin block cannot be submitted, 15-20 slides of 4-5 micron sections cut from the block should be submitted. The patient ID # should be provided with the specimens.

ELISA Assay

ELISA detection and quantification of the cytokines of interest will be performed using previously published methods. Samples will be loaded onto a 96-well microtiter plate coated with monoclonal antibody specific for the cytokine of interest. After a blocking step, samples will be diluted into a buffer and incubated with the primary antibody. After a washing step, antisera specific for the cytokine is added followed by additional incubation. Another washing step will be performed to be followed by the addition of peroxidase-conjugated secondary antibody. The concentrations of the respective cytokines will be determined in triplicate for each serum samples using an ELISA plate reader. A set of calibrators and assay controls will be run with each assay.

Immunohistochemistry (IHC) for mTOR pathway proteins and somatostatin receptor expression

Immunohistochemical detection of the mTOR pathway proteins will be carried out with the avidin-biotin technique using specific monoclonal antibodies targeting the proteins of interest. The IHC will be performed in collaboration with, [name] and on a fee-for-service basis using the personnel and resources provided by the Pathology Core facility at Emory Winship Cancer Institute. Semiquantitative scoring of protein expression will be performed by [name] (prior pathology training) in collaboration with [name] a staff anatomic pathologist with Emory University Hospital.

8 Data Review and Data Management

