Post treatment correlatives will be collected on a limited number of patients who progress on the single agent arm. These will allow us to explore whether biological mechanisms postulated to be specific to the investigational agents is involved, and if dynamic changes in putative targets distinguish between responders and non-responders in this limited subset of patients.

Analysis of baseline measurements obtained on all patients: Three types of analysis are planned: (a) Conditional analysis: does the correlate have an impact on response rate if the patient is treated with the specific investigational agent? (b) Marginal analysis: does the correlate have an impact when combining the two agents? and (c) Interaction: does the correlate have an impact differing by the treatment arm?

Due to the variability in the baseline expression of correlative endpoints such as somatostatin receptor and mTOR protein, the limited sample-size and response rate, and pre-determined sample-size, no formal power calculation is presented for this exploratory research.

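### Section 9.4 tests expression between randomised arms, which on screening archival tissue detects only chance imbalance; the analyses that could meet the exploratory objectives name only response rate and are not carried into 9.4

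*Combined protocol and SAP*

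**What the plan says.** The first exploratory objective in Section 3.3 is to "Correlate the level of expression of mTOR pathway signaling proteins in archival tumor tissue with the clinical activity of everolimus". The second does the same for somatostatin receptor and IGF1-R expression and pasireotide.

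Section 7.7.1 describes the material as "Archival paraffin embedded tissue collected at the time of patient screening". Section 4 allocates patients at random: "Randomization is conducted with a block of 3 patients in order to balance the enrollment in each arm".

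Section 9.4 lists the somatostatin receptor and 15 proteins, whose expression "in archival tissue and in fresh tumor biopsy obtained at the time of progression will be determined by immunohistochemistry". The next sentence gives the test: "Differences in mean expression between the 3 treatment arms will be compared with ANOVA or Chi-Square test". It is followed by a longitudinal mixed-model analysis relating treatment arm to change in circulating IGF-1 and in the immunoscore of progressing patients.

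The opening of Section 9 separately plans three analyses of baseline measurements on all patients: conditional, marginal and interaction by arm. The conditional one asks: "does the correlate have an impact on response rate if the patient is treated with the specific investigational agent". The other two name no outcome, and none of the three names a model, test, cut-point or multiplicity rule. The same section calls the correlative work exploratory and gives no power calculation for it. On later samples it says: "Post treatment correlatives will be collected on a limited number of patients who progress on the single agent arm".

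**The concern.** The objectives ask whether expression goes with drug activity. The test named in Section 9.4 asks whether expression differs between groups formed by randomisation. On tissue taken before treatment, the second question has a known answer: any difference is chance. A chi-square test also does not compare means, so the scale of the outcome is unsettled.

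An analyst working from Section 9.4 would run a set of uninformative baseline tests and find no specification for the analyses that matter. If response rate, the one outcome named in Section 9, is then used by default, each arm has only a handful of responders, and tumour-size data already being collected go unused.

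**Working it through.** The documents give no power figure for the correlatives, so there is none to reproduce. The checks below are illustrations with stated assumptions.

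**1. Does the between-arm test respond to a marker–activity link?**
- From the documents: 3 arms, 28 patients per arm, response rate 15% (Section 4, Figure 4-1).
- Assumed: a standard normal marker independent of arm, a logistic model for response with log-odds slope 0, 0.7 or 1.5 per SD, two-sided 5% tests, 10,000 simulated trials.

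| Slope | ANOVA by arm rejects | Responder v non-responder in one arm rejects |
|---|---|---|
| 0 | 5.1% | 4.7% |
| 0.7 | 4.8% | 23% |
| 1.5 | 4.9% | 64% |

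The last column is among simulated arms with at least 2 responders, about 94% of them. The ANOVA stays at its nominal level however strongly the marker predicts response. An analysis of the kind listed in Section 9 does respond.

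**2. How many responders are there?** Expected number per full arm = 28 × response rate: 28 × 0.05 = 1.4 and 28 × 0.15 = 4.2.

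**3. What does reducing tumour change to responder status cost?**
- Assumed: marker and shrinkage bivariate normal with correlation 0.3 or 0.5. A response is shrinkage in the top 5% or 15% of the distribution. All 28 patients have tissue and a post-baseline scan.
- Tests: Pearson correlation for continuous change; t-test of responders against non-responders, with no responders counted as no rejection. Both two-sided 5%.

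| Correlation | Continuous change | Responder status, rate 15% | Responder status, rate 5% |
|---|---|---|---|
| 0.3 | 35% | 16% to 17% | not used here |
| 0.5 | 80% | 40% | 20% to 21% |

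Ranges reflect simulation error between runs. At a 5% rate the Simon rule matters: an arm with no response in its first 18 patients stops, with probability 0.95^18 = 0.40. Among arms that reach stage II, power at correlation 0.5 is about 29%.

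**4. Multiplicity.** There are 16 markers (15 proteins plus somatostatin receptor). Expected false positives under 16 null tests = 16 × 0.05 = 0.8. If the tests were independent, P(at least one) = 1 − 0.95^16 = 0.56.

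**5. Which arms supply progression biopsies?** Section 9 limits post-treatment samples to some patients progressing on single-agent treatment. Section 9.4 speaks of biopsy at progression and of progressing patients with no limit by arm, and its test names 3 arms. The two statements do not agree.

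**The case against.** The strongest reply is that the between-arm test is not the whole plan. Section 9 poses the conditional, marginal and interaction questions about baseline correlates, and these do address Section 3.3. Section 9.4 also already plans a longitudinal analysis of immunoscore in progressing patients. This stands. A reader might infer that no planned analysis relates expression to activity, and the documents do not support that. What remains is that the Section 9 questions have no stated method, name only response rate, and are absent from 9.4.

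A reader might also infer that a 3-arm comparison of progression biopsies is impossible because the combination arm gives none. That treats Section 9 as overriding 9.4, and the text does not settle which governs. In such biopsies an arm difference could reflect treatment, though only in a selected group of progressors. The conflict needs resolving; it does not prove impossibility.

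Nor should one quote 0.95^28 = 0.24 as the chance that a 28-patient arm has no responders. An arm cannot reach 28 without a response in its first 18. It is likewise too strong to say that the baseline tests will produce a false positive: under independence, the chance of none is 0.44.

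Finally, response rate is a primary endpoint, and the plan openly cites limited sample size and response rate. That is fair and lowers the severity. It does not give the archival between-arm test a purpose.

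**Conclusion.** The point holds with limited scope. On archival tissue, the one test that Section 9.4 names for differences in expression detects only chance imbalance between randomised arms and cannot serve the Section 3.3 objectives. This follows from the timing of the tissue and from randomisation, and needs no assumption about effect size.

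The second part, that response rate is a weak choice of outcome, rests on assumptions. At a 15% response rate, responder status gives roughly half the power of continuous change: 16% to 17% against 35% at correlation 0.3, and 40% against 80% at 0.5. Missing tissue or scans would lower all of these, and an arm stopped at 18 patients would do worse. The documents supply neither the correlation nor the normal model.

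Severity is low. The objectives are exploratory, and neither the two-stage rule nor the selection of a winning arm uses these tests.

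**What to change.** 1. In Section 9.4, remove the between-arm test on archival tissue, or relabel it as a description of baseline expression by arm without a claim about activity.
2. Write the three Section 9 questions into 9.4 as models. Regress best percent change in the target-lesion sum (linear) and PFS (Cox) on baseline immunoscore, with mTOR pathway markers in Arms A and C, somatostatin receptor and IGF1-R in Arms B and C, and a marker-by-arm term. Keep objective response as a descriptive summary.
3. State in both Section 9 and Section 9.4 which arms supply progression biopsies. Analyse them as within-patient change under the longitudinal model already planned.

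The cost is wording and extra models on data already planned for collection, but it is not free. Sixteen markers by 2 outcomes is 32 models. Counting a main effect and an interaction in each gives up to 64 tests, or 64 × 0.05 = 3.2 expected false positives if all are null. Report the results as hypothesis-generating, with the number of tests stated or a false-discovery adjustment. Patients without tissue drop out of the marker models, and those without a post-baseline scan drop out of the percent-change model; report both counts. The interaction terms will have low power at these sample sizes.

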10.1 Declaration of Helsinki

The investigator must conduct the trial in accordance with the principles of the Declaration of Helsinki. Copies of the Declaration of Helsinki and amendments will be provided upon request or can be accessed via the website of the World Medical Association at http://www.wma.net/e/policy/17-c_e.html.

10.2 Ethics and Good Clinical Practice

This study must be carried out in compliance with the protocol and the principles of Good Clinical Practice, as described in Novartis standard operating procedures and:

ICH Harmonized Tripartite Guidelines for Good Clinical Practice 1996.

Directive 91/507/EEC, The Rules Governing Medicinal Products in the European Community.

US 21 Code of Federal Regulations dealing with clinical studies (including parts 50 and 56 concerning informed consent and IRB regulations).

Declaration of Helsinki and amendments, concerning medical research in humans

(Recommendations Guiding Physicians in Biomedical Research Involving Human Subjects).

The investigator agrees to adhere to the instructions and procedures described in it and thereby to adhere to the principles of Good Clinical Practice that it conforms to.

10.3 Protocol Modification

Any change or addition (excluding administrative) to this protocol requires a written protocol amendment that must be reviewed by Novartis and the investigator before implementation. Amendments significantly affecting the safety of subjects, the scope of the investigation or the scientific quality of the study require additional approval by the IRB at each study center. A

copy of the written approval of the IRB must be provided to Novartis. Examples of amendments requiring such approval are:

1. increases in drug dose or duration of exposure of subjects,
2. significant changes in the study design (e.g. addition or deletion of a control group),
3. increases in the number of invasive procedures,
4. addition or deletions of a test procedure required for monitoring of safety.

These requirements for approval should in no way prevent any immediate action from being taken by the investigator or by Novartis in the interests of preserving the safety of all patients included in the trial. If an immediate change to the protocol is felt to be necessary by the investigator and is implemented for safety reasons Novartis must be notified and the IRB at the center must be informed immediately. Amendments affecting only administrative aspects of the study do not require formal protocol amendments or IRB approval but the IRB must be kept informed of such administrative changes. Examples of administrative changes not requiring formal protocol amendments and IRB approval include:

1. changes in the staff used to monitor trials
2. minor changes in the packaging or labeling of study drug.

11 Regulatory Considerations

11.1 Institutional Review Board/Ethics Committee approval

The protocol for this study has been designed in accordance with the general ethical principles outlined in the Declaration of Helsinki. The review of this protocol by the IRB/EC and the performance of all aspects of the study, including the methods used for obtaining informed consent, must also be in accordance with principles enunciated in the declaration, as well as ICH Guidelines, Title 21 of the Code of Federal Regulations (CFR), Part 50 Protection of Human Subjects and Part 56 Institutional Review Boards.

Before implementing this study, the protocol, the proposed informed consent form and other information to subjects, must be reviewed by a properly constituted Institutional Review Board/Independent Ethics Committee/Research Ethics Board (IRB/IEC/REB). A signed and dated statement that the protocol and informed consent have been approved by the IRB/IEC/REB must be given to Novartis before study initiation. Any amendments to the protocol, other than administrative ones, must be reviewed by Novartis approved by this committee.

The Investigator will be responsible for preparing documents for submission to the relevant IRB/EC and obtaining written approval for this study. The approval will be obtained prior to the initiation of the study.

The approval for both the protocol and informed consent must specify the date of approval, protocol number and version, or amendment number.

Any amendments to the protocol after receipt of IRB/EC approval must be submitted by the Investigator to the IRB/EC for approval. The Investigator is also responsible for notifying the

IRB/EC of any serious deviations from the protocol, or anything else that may involve added risk to subjects.

Any advertisements used to recruit subjects for the study must be reviewed and approved by the IRB/EC prior to use.

11.2 Informed consent

The Investigator must obtain informed consent of a subject or his/her designee prior to any study related procedures as per GCPs as set forth in the CFR and ICH guidelines.

Documentation that informed consent occurred prior to the subject's entry into the study and the informed consent process should be recorded in the subject's source documents. The original consent form signed and dated by the subject and by the person consenting the subject prior to the subject's entry into the study, must be maintained in the Investigator's study files.

The investigator must explain to each subject (or legally authorized representative) the nature of the study, its purpose, the procedures involved, the expected duration, the potential risks and benefits involved and any discomfort it may entail. Each subject must be informed that participation in the study is voluntary and that he/she may withdraw from the study at any time and that withdrawal of consent will not affect his/her subsequent medical treatment or relationship with the treating physician.

This informed consent should be given by means of a standard written statement, written in non-technical language. The subject should read and consider the statement before signing and dating it, and should be given a copy of the signed document. If the subject cannot read or sign the documents, oral presentation may be made or signature given by the subject's legally appointed representative, if witnessed by a person not involved in the study, mentioning that the patient could not read or sign the documents. No patient can enter the study before his/her informed consent has been obtained.

The informed consent form is considered to be part of the protocol, and must be submitted by the investigator with it for IRB/IEC/REB approval.

